2 SUMMARY OF CHANGES

The initial statistical analysis plan (SAP) was signed on 25 June 2020 for an interim clinical study report requested by the European Medicines Agency Pediatric Committee. The changes made to the SAP for the final 190-203 clinical study report (CSR) are described below.

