Appendix 3: Matching of Study 190-901 and Study 190-203 subjects

- Matching criteria were updated (1) to add the tie-breaking criterion of most recent birthdate; and (2) to add onset and first seizure age as the first two tie-breaking criteria, with the further requirement that subjects with onset and first seizure ages greater than the age of their match are set to missing.

Section of 13.1.2 Sensitivity Analysis Methods(s)

- An additional sensitivity analysis was added to repeat the primary analysis, but without the use of weights, for the rate of ML decline.
- Time to unreversed ML score of zero was added as an analysis.

Section 13.3.3 Denver II Developmental scale

- Description for Denver Development Scale was updated. Additional summary for overall interpretation was added.

Section 13.3 Exploratory Endpoints

- All patient reported outcome endpoints, except for Denver II, will be listed only.

Section 13.4 Examination of Efficacy by Subgroup.

- The summary of ML scores and MRI parameters over study time will be repeated for the subgroups of baseline age <2, <3, and ≥3 years.

Section 14.4 Electrocardiogram (ECG)

	BMN 190-203 Statistical Analysis Plan, Version 2.0	Pg. 9 of 53
---	---	-------------

- Additional analyses have been added, including summary of the subjects with one or more abnormal ECGs, and a data listing for subjects with clinically significantly abnormal 3-/5-lead ECG data.

Draft

	BMN 190-203 Statistical Analysis Plan, Version 2.0	Pg. 10 of 53
---	---	--------------

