3.6.1 Interim Analysis

No formal interim analyses were planned. Analyses were produced for a biologics licensing application to FDA based on visits through November 01, 2016. Analyses were produced for purpose of regulatory reporting and congress presentations based on data through April, years 2018, 2019, 2020, and 2021. An interim clinical study report (CSR) based on visits up to 26 April 2020 was produced at the request of the European Medicines Agency Paediatric Committee. This interim report included safety and the following efficacy analyses:

- Summary statistics ML rate of decline
- Summary statistics ML rate of decline subset to baseline ML<6
- Summary statistics ML rate of decline subset to baseline ML=6
- Kaplan-Meier time to unreversed ML 2-point decline or score of zero
- Kaplan-Meier time to MLVS<12 for patients with baseline MLVS=12
- ML summary statistics by visit
- M, L, V (Vision), and S (Seizure) score summary statistics by visit
- MLV and MLVS (Motor-Language-Vision-Seizure) summary statistics by visit
- MRI parameter summary statistics by visit
- Immunogenicity
- Adverse events
- Clinical Laboratory Tests
- Vitals signs
- Electrocardiogram (ECG)
- Electroencephalograms (EEG)
- Neurological Examination

	BMN 190-203 Statistical Analysis Plan, Version 2.0	Pg. 14 of 53
---	---	--------------

- Cerebrospinal Fluid Surveillance (CSF)

The analyses of ML, MLVS, S also included matched analyses with natural history data.

There is no Data Monitoring Committee. However, BioMarin has convened a Data Review Board of internal and external experts to assist the Medical Monitor in assessing data.

Early stopping is to be considered based on clinical judgment; no inferential stopping rules are being employed.

Draft

	BMN 190-203 Statistical Analysis Plan, Version 2.0	Pg. 15 of 53
---	---	--------------

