13 EFFICACY EVALUATIONS

The efficacy analyses will be based on the ITT population. The PP population will be used for sensitivity analyses of the primary endpoint.

There will be two sets of efficacy analyses. The first set will be descriptive summaries of the Study 190-203 subjects at baseline and follow-up visits for all efficacy endpoints. The second set of analyses are for the CLN2 scales M, L, V, S, ML, MLV, and MLVS and based on matching Study 190-203 subjects to Study 190-901 historical controls. These will include descriptive summaries and statistical model results for treatment comparison to natural history. If natural history data are available on siblings with disease, data of sibling pairs will be presented in listings and graphical displays.

The primary efficacy endpoint is the rate of decline in the 0 to 6-point ML score and the primary analysis is based on matching with Study 190-901 subjects. All matched analyses will be based on a single matched set and the algorithm for matching has been prespecified prior to any matched analyses and is described in [Appendix 3](#). The matching will be a 3-1 matching of the Study 190-901 Evaluable population and the Study 190-203 ITT population. The matching criteria are:

- Equal ML score
- Age within 3 months
- Genome: equal number of common alleles (c.622C→T, c.509.1G→C)

For all matched analyses, Study 190-901 subjects will be weighted inversely to the number of Study 190-901 subjects matched to a given Study 190-203 subjects. The weights for 3, 2, and 1 Study 190-901 subject(s) matched to a given Study 190-203 subject will be 1/3, 1/2, and 1 respectively and the weights are normalized to the number of Study 190-901 subjects matched to Study 190-203 subjects.

To demonstrate comparability of the matched groups, summaries of the following variables will be produced for each group, with Study 190-901 subjects weighted according to number of matches.

- Age (years, continuous)
- Sex (Female/Male)
- Genome
- Site / Region
- M, L, ML, MLVS scale scores

	BMN 190-203 Statistical Analysis Plan, Version 2.0	Pg. 27 of 53
---	---	--------------

- Age of diagnosis (years)
- Age of first symptoms (years)

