- For the selected Study 190-203 subject, match with the Study 190-901 subject who has not yet been matched and has a (ML, age of assessment) combination that minimizes the distance measure. There may be greater than one Study 190-901 subject that satisfies minimal distance, in which case choose the 190-901 subject who has fewest potential Study 190-203 matches based on the distance ≤ 3 points (and ≤ 2 , ≤ 1 , ≤ 0 as needed). If there are no Study 190-901 subjects who satisfy distance ≤ 3 , then there is no match for the Study 190-203 subject.
- It is possible that there remains greater than one 901 patients selected. In this situation, ties are broken down based on the following criteria ordered: onset age, seizure age, exact genome, sex, country, most recent date of birth. For Study 203 patients missing onset (seizure) age, matching 901 patient(s) must have missing onset (seizure) age or onset (seizure) age after age of match.

	BMN 190-203 Statistical Analysis Plan, Version 2.0	Pg. 51 of 53
---	---	--------------

Repeat till all Study 190-203 subjects have been attempted for match. This completes a 1-1 matching. To attain 3-1 matching, cycle through the Study 190-203 subjects twice more. Study 190-203 subjects will have 3, 2, 1, or 0 Study 190-901 subjects matched. We refer to the group as a matched set. For analysis purposes, Study 190-203 subjects will have a weight of one and Study 190-901 subjects will be weighted inversely to the number of matches (1/3, 1/2, 1) and the weights will be normalized to the number of Study 190-901 subjects matched to Study 190-203 subjects.

Draft

BIOMARIN®	BMN 190-203 Statistical Analysis Plan, Version 2.0	Pg. 52 of 53
------------------	---	--------------

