12 EFFICACY EVALUATIONS

The efficacy analyses will be based on the ITT population. The PP population will be used for sensitivity analyses of the primary endpoint.

There will be two sets of efficacy analyses. The first set will be descriptive summaries of the Study 203 patients at baseline and follow-up visits for all efficacy endpoints. The second set of analyses are for the CLN2 scales M, L, V, S, ML, MLV, and MLVS and based on matching Study 203 patients to Study 901 historical controls. These will include descriptive summaries and statistical model results for treatment comparison to natural history. If natural history data are available on siblings with disease, data of sibling pairs will be presented in listings and graphical displays.

The primary efficacy endpoint is the rate of decline in the 0 to 6-point ML score and the primary analysis is based on matching with Study 901 patients. All matched analyses will be based on a single matched set and the algorithm for matching has been prespecified prior to any matched analyses and is described in [Appendix 3](#). The matching will be a 3-1 matching of the Study 901 Evaluable population and the Study 203 ITT population. The matching criteria are:

- Equal ML score
- Age within 3 months
- Genome: equal number of common alleles (c.622C→T, c.509.1G→C)

For all matched analyses, Study 901 patients will be weighted inversely to the number of Study 901 subjects matched to a given Study 203 patient. The weights for 3, 2, and 1 Study 901 patient(s) matched to a given Study 203 patient will be 1/3, 1/2, and 1 respectively and the weights are normalized to the number of Study 901 patients matched to Study 203 patients.

To demonstrate comparability of the matched groups, summaries of the following variables will be produced for each group, with Study 901 patients weighted according to number of matches.

- Age (years, continuous)
- Sex (Female/Male)
- Genome
- Site / Region
- M, L, ML, MLVS scale scores
- Age of diagnosis (year)
- Age of first symptoms (year)

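### SAP Section 13 says the matching algorithm was fixed before any matched analysis, but its tie-breaks were revised after the interim matched analyses and no planned run uses the June 2020 rules

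*SAP*

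**What the plan says.** The primary analysis compares the rate of ML decline in treated children with that in matched Study 190-901 controls. SAP v2.0 Section 13 says of the matching that "the algorithm for matching has been prespecified prior to any matched analyses", and refers to Appendix 3. The same words stand in Section 12 of the SAP dated 25 June 2020: "All matched analyses will be based on a single matched set and the algorithm for matching has been prespecified prior to any matched analyses".

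v2.0 Section 2 gives the history: "The initial statistical analysis plan (SAP) was signed on 25 June 2020 for an interim clinical study report". Section 3.6.1 reports that interim report in the past tense and adds: "The analyses of ML, MLVS, S also included matched analyses with natural history data".

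For the final report, the Appendix 3 entry in Section 2 lists these changes to matching: "to add the tie-breaking criterion of most recent birthdate"; "to add onset and first seizure age as the first two tie-breaking criteria"; and, attached to the second, "with the further requirement that subjects with onset and first seizure ages greater than the age of their match are set to missing".

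The sensitivity analyses in Section 13.1.2 are a per-protocol repeat, a sign test, the ML<6 and ML=6 subsets, summaries for all treated versus matched treated children, and an unweighted repeat. None re-matches the final data under the June 2020 appendix.

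**The concern.** In a single-arm study compared with a registry, the choice of controls takes the place that randomisation would have. A statement that the selection rule was fixed before anyone saw a matched result is therefore a real safeguard, and a reader of the final report will rely on it. The sentence was written for the June 2020 rules and kept after those rules had been used and part of them revised. v2.0 thus claims for its current algorithm a protection that only its unchanged core has. Because no planned run applies the June rules to the final data, the report will not show whether the revision moved the estimate.

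**Working it through.** The plan states no figure on this point, so the check is a comparison of texts followed by an illustration of size.

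**1. Order of events.** The June 2020 SAP was written for the interim report. That report used visits up to 26 April 2020 and included matched ML, MLVS and S analyses. v2.0 describes the report as already produced, and Section 3.6.1 also mentions analyses of data through April 2021. So v2.0 postdates the interim matched analyses. Both versions of Appendix 3 allow for up to 14 matched pairs, and the June text already says that every enrolled patient had received drug. The treated children were therefore known when the rules were revised.

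**2. Tie-breaks among equally close controls.** v2.0 introduces this step with "It is possible that there remains greater than one 901 patients selected". The two orders are:

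| Position | June 2020 | v2.0 |
|---|---|---|
| 1 | exact genome | onset age |
| 2 | sex | seizure age |
| 3 | seizure age | exact genome |
| 4 | onset age | sex |
| 5 | country | country |
| 6 | birthdate, no direction given | birthdate, most recent |

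Only position 5 is unchanged. Section 2 describes onset and seizure age as added, but the June list already had them in 4th and 3rd place, so they were moved up. The condition for treated children with missing onset or seizure age is new. From its place in Appendix 3 and its description in Section 2, it acts among controls that are still tied.

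**3. Order of treated children.** The match is greedy and without replacement, so the order in which treated children are taken can decide who gets which control. Both versions take first the child with the fewest candidates within 3 months, then break ties at 2, 1 and 0 months. The June text has one further rule, based on the mean distance of the candidate controls. That rule is absent from v2.0, and Section 2 does not mention it. If ties remain after the 0-month step, v2.0 does not determine the match.

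**4. What did not change.** Equal ML score, age within 3 months, equal number of common alleles, the 3-1 ratio and the weights are the same in both versions.

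**5. Size, as an illustration.** Protocol Section 7.2 gives mean (SD) decline per 48 weeks of 0.27 (0.35) in treated children and 2.12 (0.98) in 42 historical controls, a difference of 1.85. Assume these apply here.

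*Share of one control.* With S matched sets and m controls in a given set, one control carries 1/(S × m) of the weighted control mean. Replacing it by a control whose rate differs by 1 SD shifts that mean by 0.98/(S × m):
- 14 sets, m = 3: 0.98/42 = 0.023
- 14 sets, m = 1: 0.98/14 = 0.070
- 10 sets: 0.98/30 = 0.033 for m = 3, and 0.98/10 = 0.098 for m = 1
- one such swap, in the same direction, in every set of 3: 0.98/3 = 0.33

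*Overall test.* For an unequal-variance t-test with 14 treated children and n controls, SE = √(0.35²/14 + 0.98²/n):

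| n | SE | df | t = 1.85/SE | Smallest significant difference |
|---|---|---|---|---|
| 42 | 0.178 | 53.6 | 10.4 | 0.36 |
| 28 | 0.207 | 37.5 | 8.9 | 0.42 |
| 14 | 0.278 | 16.3 | 6.65 | 0.59 |

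*Extreme bound.* Let a share p of the control weight be replaced by controls with zero decline. The control mean becomes 2.12(1 − p) and the variance (1 − p)(0.98² + 2.12²) − mean². Two-sided significance at 0.05 is lost only at p of about 0.69 (n = 42), 0.645 (n = 28) or 0.525 (n = 14).

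*ML=6 subset.* The documents do not give the number of sets. If it is 5 to 8, one 1-SD swap shifts the control mean by 0.98/(8 × 3) = 0.041 to 0.98/(5 × 1) = 0.196. Ties may be more frequent here: registry ages are in months, and Appendix 3 lets a first ML score of 6 be carried back to earlier ages, so several controls could reach zero distance. That is an inference, because the number of ties is not stated.

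**The case against.** The strongest reply is that this is a disclosed and permitted refinement. Protocol Section 14.1 requires the SAP only before final database lock and lets it prevail over the protocol. Section 2 logs the new order, the birthdate direction and the missing-age condition. The three criteria listed just after the disputed sentence are unchanged. Giving birthdate a direction is a clarification, and ranking onset and seizure age first may improve comparability. Section 13 also plans balance summaries that include age at first symptoms. All of this stands. It does not make the Section 13 sentence true of the appendix it cites, and that sentence is not limited to final-data analyses.

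Four stronger readings might be inferred and are not supported:
- *The change was driven by results, or favours the drug.* Nothing in the documents shows this.
- *Using different controls in the interim and final reports breaks the promise of a single matched set.* In context, that phrase governs the analyses within one plan. Controls could also differ under unchanged rules. Appendix 3 caps control follow-up at that of the treated child and refuses matches with under 6 months, so longer treated follow-up can admit more controls. Protocol Section 11.1 says the registry was still adding patients.
- *The last ordering rule was deliberately removed.* The text shows only that it is absent. The omission may be editorial, and the program may still apply the rule.
- *The primary test could flip.* The bound above makes that implausible.

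**Conclusion.** The point holds as an inaccurate prespecification statement together with a missing sensitivity run. The statement is fair for the core criteria, the ratio and the weights. It is wrong for the tie-breaks and the missing-age condition. The unlogged absence of the last ordering rule is a separate, smaller gap, which matters only if treated children remain tied.

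The effect on the overall test is probably negligible. The effect on the ML=6 subset is unknown, because neither the number of ties nor the number of sets is given.

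Two assumptions limit this. The size figures borrow means and SDs from an earlier study that enrolled children aged 3 or more, and these may not describe young ML=6 controls. The June text available for comparison is labelled Version Final Draft and dated 25 June 2020; the comparison takes its Appendix 3 to be that of the SAP signed on that date.

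**What to change.** 1. **Reword Section 13**, for example: *The core matching criteria, the 3-1 ratio and the weights were set in the SAP of 25 June 2020. After the interim matched analyses, v2.0 revised the tie-breaks by ranking onset age and seizure age first, specifying the direction for birthdate, and adding a condition for treated subjects with missing onset or seizure age.* Give the reason for the revision.
2. **Add to Section 13.1.2** a repeat of the primary analysis, and of its ML=6 and ML<6 subsets, on the final data with the matched set produced by the June 2020 Appendix 3 rules. State the birthdate direction used, since the June text gives none. Report both estimates and the number of controls that differ. This isolates the rule change on final data; it does not separate every source of difference between the interim and final reports.
3. **State in Appendix 3** a deterministic last rule for ordering tied treated children, and log in Section 2 whether the June rule was dropped or is retained.

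The cost is a few sentences and one extra run, plus some reprogramming if the interim matching code was not kept. The prespecification statement becomes less favourable but accurate.

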13.1 Primary Efficacy Endpoint(s)

The primary efficacy endpoint is the rate of decline in the 0 to 6-point ML score, measured in units of 48 weeks. Since the endpoint is a rate of decline, as opposed to a rate of change, it is expected to be a positive number, with larger values representing a steeper deterioration of clinical status over time. The rate of decline will be estimated for each subject.

13.1.1 Primary Analysis Method

The mean rate of decline in treated subjects will be compared to the mean rate of decline in untreated subjects using a 2-sample t-test. The null and alternative hypotheses to be tested are:

$$H_0: \mu_{190-203} = \mu_{190-901}$$

$$H_1: \mu_{190-203} \neq \mu_{190-901}$$

where $\mu_{190-203}$ represents the population mean rate of decline in the BMN 190-treated population and $\mu_{190-901}$ represents the population mean rate of decline in Study 901.

Testing will use the two-sample T-test with unequal variance and will be conducted at the two-sided $\alpha=0.05$ significance level. The T-test will weight Study 190-901 subjects according to the number of matches: weights 1/3, 1/2, 1 for 3, 2, 1 matches respectively. The weights will be normalized to sum to the total number of Study 190-901 subjects matching to Study 190-203 subjects. Treatment effect will be estimated as the difference in the mean rate of decline: Study 190-901 versus Study 190-203 subjects. The primary analysis will be based on the matched ITT population. Details of the slope estimation is given in [Appendix 2](#).

13.1.2 Sensitivity Analysis Method(s)

The rate of ML decline endpoint will also be analyzed as follows:

- Repeat primary analysis (T-test) on the PP population by removing any matched set where the Study 190-203 member is not within the PP population.
- Test difference in rate of ML decline using the Sign test (Binomial) for the ITT and PP populations. The slope for each matched Study 190-203 patient is compared to the average slope of the Study 190-901 subject (s) of the 3-1 matched set.
- Repeat primary analysis on the baseline ML<6 population and baseline ML=6 population

	BMN 190-203 Statistical Analysis Plan, Version 2.0	Pg. 28 of 53
---	---	--------------

- If not all Study 190-203 subjects have at least one Study 190-901 match, produce summary statistics for the rate of ML decline for the ITT and matched Study 190-203 populations.
- Repeat primary analysis but without the use of weights (equal weighting)

Analyses of other measures of ML change are outlined in the next subsections and are based on the ITT population with matching.

13.1.3 Time to Unreversed 2-point Decline or Score of Zero

Response defined as the absence of an unreversed two-point decline or score of zero in ML score by last assessment relative to baseline, will be analyzed using Kaplan-Meier methods and the Cox proportional hazards model. An unreversed two-point decline is defined as any decline of 2 points or more that had not reverted to a 1-point decline (or better) as of the last recorded observation. An unreversed score of zero is a score of zero that did not subsequently increase to a score greater than zero as of the last recorded observation.

The Cox model will include an indicator variable for study group and no additional covariates since the study groups are matched on the important variables. Kaplan-Meier curves will be produced for the two matched cohorts. Time from baseline to the first unreversed 1-point decline in ML score will also be displayed by Kaplan-Meier method. The Cox model and Kaplan-Meier curves will weight Study 190-901 subjects according to the number of matches: weights 1/3, 1/2, 1 normalized to the number of Study 190-901 subjects matched to Study 190-203 subjects, for 3, 2, 1 matches, respectively.

